9.2.1. Inclusion criteria

Patients must meet all of the following inclusion criteria to be eligible for inclusion in the study:

- Have their first reimbursed prescription of tofacitinib (Anatomical Therapeutic Chemical [ATC] code L04AA29) during the indexing period;
- Have 12 months of available medical history *prior to* the index tofacitinib dispensing; and
- Have 12 months of available medical data *after* the index tofacitinib dispensing.

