9.2.3. Study period

The study period will be from 01 January 2017 to 31 December 2025. The **indexing period** will begin on 01 January 2018 (the earliest date of the full distribution of the original aRMM materials for France [RA], aligned with the first reimbursed prescription record in the French database), will end on 31 December 2024, and will be used to identify patients who newly initiated tofacitinib. The date of a patient's first reimbursed prescription of tofacitinib during the indexing period will be considered the patient's **index date** (Figure 2).

Figure 2. Example index tofacitinib dispensing and patient-specific study period against the Venous Thromboembolism Reporting Periods

^{*} Aligned with the first reimbursed prescription record in the French database

The 12-month **baseline period** will immediately precede the index date and will be used to ascertain indication (including off-label use), comorbidities, prior and current medications, potential contraindicated use of tofacitinib, VTE risk factors, CV risk factors, malignancy risk factors, use in patients aged 65 years and older and whether there is evidence that prescribers are following the recommended screenings in the aRMM materials that should occur *prior to* initiation of tofacitinib.

The 12-month **follow-up period** will begin on the patient's index date. Variables that will be ascertained during the follow-up period include comorbidities, comedications, adherence to the recommended posology per indication (ADD) and duration of tofacitinib treatment, potential contraindicated use of tofacitinib, VTE, CV or malignancy risk factors, use with concomitant medications not compatible with tofacitinib and whether there is evidence that prescribers are following the recommended monitoring in the aRMM materials that should occur *after* initiation of tofacitinib.

[figure not shown]

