9.3. Variables

9.3.1. Variables and definitions

Table 3 summarises and defines the study variables to be collected and analysed in SNDS. Unless otherwise specified, these variables will be assessed during each patient's entire study period (baseline period and follow-up period).

This study will use code-based algorithms from the literature and/or other code lists to identify study variables. Published validated algorithms will be used where available.^{6, 7} All code-based algorithms and code lists will be reviewed and/or approved by Pfizer prior to

study initiation. Preliminary algorithms and/or codes are proposed in the following (Table 3); see also Annexes). Final algorithms and/or code lists may be refined as part of the statistical analysis plan (SAP) development. It is also to be noted that while laboratory tests performed are captured, results of laboratory tests are not available in the SNDS database.

Table 3. Operational definitions of study variables in Système National des Données de Santé

Variable	Role	Operational definition
Exposure		
Tofacitinib treatment	Exposure	Defined as having ≥1 ATC code (L04AA29) for a reimbursed prescription of tofacitinib during the indexing period. Index date is defined as the date of the first reimbursed prescription of tofacitinib.
Indication		
Indication	Indication (including off-label use)	Reported in the following categories: RA, PsA, UC and off-label/unknown based on hospital discharge diagnoses and active registration for diagnoses reported in the long-term disease (LTD) database for outpatients in the relevant time period. If there are no diagnosis codes for RA, PsA or UC, it will be categorised as off-label/unknown indications. Details will be further developed in the SAP.
		List of diagnoses codes for indications in ANNEX 13. LIST OF DIAGNOSIS CODES FOR INDICATIONS.
Primary Objective 1: I	Demographics, comorbi	dities and prior and current medications
		T OF CODES FOR COMORBIDITIES, unless otherwise
Age at tofacitinib initiation	Demographic	Calculated as the date of tofacitinib initiation minus the patient's month and year of birth and reported in the following categories: <18 years, 18-29 years and 30-39 years; 40-49 years; 50-59 years; 60-69 years; 70-79 years; ≥80 years; and <65 years and ≥65 years.
Sex	Demographic	Reported in the following categories: Male, Female and Unknown. Assessed on the date of the index tofacitinib prescription dispensing.

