no use of an		Note: This definition will miss those who have one 10 mg
alternative therapy		BID prescription and the remaining prescriptions are 5 mg
(i.e., biologic) prior to		BID.
tofacitinib initiation		
A patient who has	Outcome:	Among UC patients, is defined as ≥ 1 prescription dispensing
known VTE, CV or	Adherence to	for a biologic (as identified by ATC codes) prior to the index
malignancy risk	recommended	tofacitinib dispensing and an ADD >10 mg in any of the
factors with an ADD	posology	intervals: Weeks 17-24, Weeks 25-32, Weeks 33-40 or
of >10 mg in Weeks		Weeks 41-48 of follow-up and ≥1 VTE, CV or malignancy
17-24, Weeks 25-32,		risk factors from baseline to Week 16.
Weeks 33-40 or		
Weeks 41-48 of		An ADD \geq 15 mg in the definition above will be used in a
follow-up and with		sensitivity analysis.
evidence of a		
diagnosis for UC but		
no use of an		
alternative therapy		
(i.e., biologic) prior to		
tofacitinib initiation		

Adherence to patient screening and laboratory monitoring prior to and during tofacitinib treatment

The following recommended screenings and monitoring will be assessed in the following time frames:

- In the 30 days prior to and including the day of tofacitinib initiation;
- In the 31 to 60 days prior to tofacitinib initiation;

Table 3. Operational definitions of study variables in Système National des Données de Santé

Donnees de Sante			Donnees	
	Variable	Role		Operational definition

- In the 61 to 90 days prior to tofacitinib initiation; and
- In the 91 to 180 days prior to tofacitinib initiation;

For patients with at least 6 months of tofacitinib therapy (duration of tofacitinib therapy defined in Section 9.3.2):

- In the 60 days after the day of tofacitinib initiation;
- In the 61 to 120 days after tofacitinib initiation; and
- In the 121 to 180 days after to facitini binitiation.

For patients with 12 months of tofacitinib therapy (duration of tofacitinib therapy defined in Section 9.3.2):

- In the 181 to 240 days after tofacitinib initiation;
- In the 241 to 300 days after to facitinib initiation; and
- In the 301 to 360 days after to facitinib initiation.

For analyses, 1 month will be defined as 30 days and 1 year will be defined as 360 days.

List of laboratory codes in ANNEX 10. LIST OF LABORATORY TEST CODES.

List of laboratory codes	III THI TILL TO. LIDT	OF EMBORITORY TEST CODES.
Creatinine (serum or	Outcome:	Defined as ≥1 procedure code or ≥1 ICD-10 diagnosis code

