Continuation of	Outcome: changes	Defined as ≥1 malignancy risk factor while receiving
tofacitinib after	in use in patients	tofacitinib therapy (as listed and defined above) plus
developing ≥1	with malignancy	≥1 prescription dispensing for tofacitinib within a specific
malignancy risk	risk factor	time window after the code for the first malignancy risk
factors while taking		factor.
tofacitinib		
Adherence to recomm	endations for limitation	ons of use in the JAKi referral (will be stratified by the
JAKi report period 1,		
A patient with CV or	Outcome: changes	Defined as an UC patient having ≥1 CV or malignancy risk
malignancy risk	in use of tofacitinib	factor(s) (as listed and defined above) from baseline to week
factors, an ADD of	following updated	16 and an ADD of >10 mg in any of the intervals: Weeks 17-
>10 mg in Weeks 17-	recommendations	24, Weeks 25-32, Weeks 33-40 and Weeks 41-48 of follow-
24, Weeks 25-32,	following the JAKi	up while receiving tofacitinib therapy.
Weeks 33-40 and/or	referral	
Weeks 41-48 of		This variable will be stratified by use of an alternative
follow-up and		therapy (i.e., biologic) in the 12 months prior.
evidence of a		
diagnosis for UC		
		ons of contraindicated use
Initiating tofacitinib	Outcome:	Defined as ≥1 ICD-10 diagnosis code for severe hepatic
with severe hepatic	Contraindicated	impairment in the 12 months prior to tofacitinib initiation.
impairment	use	
Initiating tofacitinib	Outcome:	Defined as tofacitinib initiation (i.e., the index date)
while pregnant	Contraindicated	occurring between the beginning and end of a pregnancy,
	use	using SNDS-specific algorithms developed.
		Complete list of pregnancy codes in ANNEX 11. LIST OF
		CODES FOR COMORBIDITIES
Receiving tofacitinib	Outcome:	Defined as evidence of a pregnancy while receiving
while pregnant	Contraindicated use	tofacitinib therapy using SNDS-specific algorithms.
Initiating tofacitinib	Outcome:	Defined as ≥1 ICD-10 diagnosis code for TB in the 60 days
while having TB	Contraindicated	prior to tofacitinib initiation.
(active or latent)	use	

Table 3. Operational definitions of study variables in Système National des Données de Santé

Variable	Role	Operational definition
Initiating tofacitinib	Outcome:	Defined as ≥1 ICD-10 diagnosis code for a serious and/or
while having a serious	Contraindicated	opportunistic infection in the 60 days prior to tofacitinib
and/or opportunistic	use	initiation.
infection		Complete list of serious and/or opportunistic infections in

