Spontaneous abortion	O03
Medical abortion	O04
Other abortion	O05
Unspecified abortion	O06
Preterm labour and delivery	O60
Single delivery by forceps and vacuum extractor	O81
Single delivery by caesarean section	O82

Pregnancy cessation	ICD-10
Other assisted single delivery	O83
Multiple delivery	O84
Ectopic pregnancy	O00
Hydatidiform mole	O01
Other abnormal products of conception	O02
Failed attempted abortion	O07
Complications following abortion and ectopic and molar pregnancy	O08
Pre-existing hypertension complicating pregnancy, childbirth and the puerperium	O10
Pre-existing hypertensive disorder with superimposed proteinuria	O11
Gestational [pregnancy-induced] oedema and proteinuria without hypertension	O12
Gestational [pregnancy-induced] hypertension without significant proteinuria	O13
Gestational [pregnancy-induced] hypertension with significant proteinuria	O14
Eclampsia	O15
Unspecified maternal hypertension	O16
Haemorrhage in early pregnancy	O20
Excessive vomiting in pregnancy	O21
Venous complications in pregnancy	O22
Infections of genitourinary tract in pregnancy	O23
Diabetes mellitus in pregnancy	O24
Malnutrition in pregnancy	O25
Maternal care for other conditions predominantly related to pregnancy	O26
Abnormal findings on antenatal screening of mother	O28
Complications of anaesthesia during pregnancy	O29

Malignant cancer (except skin cancer)

ICD-	Description
10	
C00	Malignant neoplasm of lip
C01	Malignant neoplasm of base of tongue
C02	Malignant neoplasm of other and unspecified parts
C03	Malignant neoplasm of gum
C04	Malignant neoplasm of floor of mouth
C05	Malignant neoplasm of palate
C06	Malignant neoplasm of other and unspecified parts
C07	Malignant neoplasm of parotid gland
C08	Malignant neoplasm of other and unspecified major salivary glands
C09	Malignant neoplasm of tonsil
C10	Malignant neoplasm of oropharynx
C11	Malignant neoplasm of nasopharynx
C12	Malignant neoplasm of pyriform sinus

ICD- 10	Description
C13	Malignant neoplasm of hypopharynx
C14	Malignant neoplasm of other and ill-defined sites in the lip, oral cavity and pharynx
C15	Malignant neoplasm of oesophagus
C16	Malignant neoplasm of stomach
C17	Malignant neoplasm of small intestine
C18	Malignant neoplasm of colon
C19	Malignant neoplasm of rectosigmoid junction
C20	Malignant neoplasm of rectum
C21	Malignant neoplasm of anus and anal canal
C22	Malignant neoplasm of liver and intrahepatic bile
C23	Malignant neoplasm of gallbladder

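### Pregnancy during tofacitinib treatment is searched only within the 12-month follow-up, with a code list that lacks single spontaneous delivery, so contraindicated use is understated by an unknown amount

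*Protocol*

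**What the plan says.** Table 3 (Section 9.3.1) has two pregnancy measures under contraindicated use.

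- *Initiating tofacitinib while pregnant* requires an index date "occurring between the beginning and end of a pregnancy". This row points to Annex 11 for the pregnancy codes.
- *Receiving tofacitinib while pregnant* is "Defined as evidence of a pregnancy while receiving" "tofacitinib therapy using SNDS-specific algorithms". This row names no window and no code list. Section 9.7.2.3.1 words the measure as receipt of the drug during pregnancy and cites two claims-based pregnancy algorithms.

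The window comes from three places. Section 9.2.3 sets a 12-month follow-up from index and includes among its variables "potential contraindicated use of tofacitinib, VTE, CV or malignancy risk factors, use with concomitant medications not compatible with tofacitinib". Section 9.3.1 adds the default that, unless a row says otherwise, "these variables will be assessed during each patient's entire study period (baseline period and follow-up period"). Section 9.2.1 requires of each patient: "Have 12 months of available medical data *after* the index tofacitinib dispensing". No section extends the search for pregnancy outcomes past month 12.

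Annex 11 gives one pregnancy list, under a heading about pregnancy cessation. Its delivery entries go from preterm labour and delivery (O60) straight to "Single delivery by forceps and vacuum extractor" (O81), then caesarean, other assisted and multiple delivery (O82 to O84). Single spontaneous delivery (O80) is absent.

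**The concern.** A pregnancy conceived on treatment often ends after the 12-month window has closed. If it is uncomplicated, nothing in the listed codes flags it before delivery. If it ends inside the window in an uncomplicated single vaginal birth, nothing in the listed codes flags it at delivery either. Capture is then tilted towards losses and complicated pregnancies.

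This is one of the five contraindicated-use measures in Section 9.7.2.3.1, in a study whose research question is whether prescribers adhere to the risk minimisation materials. Under-counting makes adherence look better than it is. Section 9.9.1.1 acknowledges a proxy that errs the other way, by overestimating non-adherence. Section 9.9 does not mention this one.

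**Working it through.** The protocol states no expected number of pregnancies, no algorithm sensitivity and no persistence figure, so there is no figure of its own to reproduce. Two checks are possible.

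**1. What the code list contains (Annex 11)**

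- Endings or losses: O00 to O08 (9 categories), O60 (1), O81 to O84 (4). Total 14 of 30, or 47%.
- Conditions during pregnancy: O10 to O16 (7), O20 to O26 (7), O28 and O29 (2). Total 16 of 30, or 53%. All are complications or abnormal findings. There is no entry for routine antenatal supervision.
- Section 9.9.1.2 says outpatient ICD-10 information comes only from long-term disease registration. In practice these codes therefore need a hospital record or such a registration.

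**2. How many pregnancies end after the window**

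Inputs from the protocol: follow-up T of 12 months, taken as 365 days, and also as 360 days because Table 3 says "1 month will be defined as 30 days and 1 year will be defined as 360 days".

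Assumptions, none given in the protocol:

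- term at G = 266 days from conception, or 280 from last period;
- a share e of pregnancies ending early, at g = 42 to 70 days from conception;
- a proportion p still on drug at 12 months, with exponential decline.

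Share ending after follow-up = 1 − [(1 − e)·F(T − G) + e·F(T − g)], where F(t) = t/T under full persistence. Otherwise F(t) = (1 − exp(−λt)) / (1 − exp(−λT)), with λ = −ln(p)/T.

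*Term pregnancies, even conception, full persistence.* The share reduces to G/T.

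- T = 365: 266/365 = 73% and 280/365 = 77%. Only pregnancies starting by day 365 − 280 = 85 to 365 − 266 = 99 reach term inside the window.
- T = 360: 266/360 = 74% and 280/360 = 78%.

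*All pregnancies, G = 266, T = 360 to 365:*

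| Early endings (e) | p = 100% | p = 50% | p = 30% |
|---|---|---|---|
| 0% | 73–74% | 66–67% | 60–62% |
| 15% | 64–66% | 57–59% | 52–54% |
| 30% | 55–58% | 49–51% | 44–46% |

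Worked corner (p = 30%, e = 30%, g = 42, T = 365): λ = 1.204/365 = 0.0033; F(99) = 0.398; F(323) = 0.936; share = 1 − (0.7 × 0.398 + 0.3 × 0.936) = 44%. A more extreme e of 50% with p = 30% gives 33–36%.

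*Pregnancies already under way at index.* A term pregnancy of this kind ends within about 266 days of index, which is inside the window. *Initiating tofacitinib while pregnant* is therefore not truncated, but the missing delivery code still affects it.

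**3. What the planned data could cover**

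The study period ends on 31 December 2025. Subtracting 12 + 10 = 22 months gives end February 2024. January 2018 to February 2024 is 74 of the 84 indexing months (88%), which leaves the last 10 months incompletely covered. This is a share of calendar months, not of patients.

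**The case against.** The strongest reply is that the protocol leaves the algorithm open. The receiving row asks for evidence of a pregnancy, not a completed one, and does not itself cite Annex 11. Section 9.3.1 calls algorithms and codes preliminary and lets the SAP refine them. Section 9.9.1.2 says algorithms will also draw on procedures and reimbursed prescriptions where relevant. This stands as a reason why the size of the error cannot be stated. It does not remove the problem: the adjacent row treats Annex 11 as the complete pregnancy list, there is no other, and no algorithm finds an outcome that lies outside the period it searches. The titles of the two cited algorithm papers also refer to pregnancy outcomes.

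Four stronger readings are tempting and are not supported.

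- A reader might take the Annex 11 heading to mean that the list is mainly end-of-pregnancy codes. By count it is not: 16 of 30 are antenatal conditions that can flag an ongoing pregnancy.
- A reader might infer that most pregnancies conceived on treatment go unseen. The 73–77% is for term pregnancies under even conception and full persistence. The share of all pregnancies can fall below half, and ending after month 12 does not by itself mean undetected.
- A reader might expect the measure to come out near zero whatever prescribers do. Early losses, complicated pregnancies and some deliveries remain visible, and the documents give no rate from which to argue that.
- A reader might think the code itself must fall while the woman is on the drug. Section 9.7.2.3.1 describes overlap of treatment and pregnancy, which is the sensible reading.

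**Conclusion.** The point holds in limited form. The 12-month window without run-out and the missing delivery code are both in the text, and both push towards under-counting pregnancy exposure. Under the stated assumptions about 73–77% of term pregnancies starting in follow-up end after it. Allowing for early losses and lower persistence, the share of all pregnancies ending after it can be about 45%. These are shares ending outside observation, not shares missed; the shortfall itself depends on an algorithm the protocol does not specify. The bias has a known direction and an inexpensive remedy, so it deserves correction despite the preliminary status of the code lists.

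**What to change.** - Add single spontaneous delivery (O80) to the Annex 11 pregnancy list. This serves both pregnancy measures.
- For *Receiving tofacitinib while pregnant* only, search pregnancy-outcome codes for 10 months beyond the 12-month follow-up, capped at 31 December 2025. Ten months exceeds the 266 to 280 days needed by a pregnancy starting on the last day of follow-up.
- Date the start of pregnancy backwards with the cited algorithm. Count the woman if any part of the pregnancy overlaps tofacitinib exposure in the 12-month follow-up, wherever the outcome code falls.
- Report women indexed after about end February 2024, or without data through the extension, as incompletely observed. Section 9.2.1 guarantees only 12 months of data after index.
- State the remaining truncation in Section 9.9.

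The cost is one changed search window, one added code, a small amount of extra analysis, and incomplete capture for the women just described. The data lie within the planned study period. The window should be settled before the extraction criteria in Section 9.6 are final.

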		ANNEX 3. LIST OF DIAGNOSIS CODES FOR SELECT
		INFECTIONS OF INTEREST
Adherence to recommo	endations for limitation	ons of use with concomitant medications not compatible
with tofacitinib		
Variables will be presen	ted overall and may be	e stratified by patients with and without ≥2 tofacitinib
prescription reimbursem	ents during the follow	-up period (where the second prescription is reimbursed within
	f the days' supply [or t	the equivalent] of the first prescription), pending sufficient
sample size.		
Use of biologics	Outcome:	Defined as ≥30 overlapping days' supply of a tofacitinib
approved to treat RA,	Concomitant	prescription dispensing and a prescription dispensing for a
PsA or UC while	medications not	biologic approved to treat RA, PsA or UC (as identified by
taking tofacitinib	compatible with	ATC code[s]) during the follow-up period.
	tofacitinib	Complete list of biologics in ANNEX 7. LIST OF ATC
		CODES FOR MEDICATIONS OF INTEREST TO AVOID
		WHILE TAKING TOFACITINIB.
Use of selected potent	Outcome:	Defined as ≥30 overlapping days' supply of a tofacitinib
immunosuppressants	Concomitant	prescription reimbursement and a prescription reimbursed
while taking	medications not	for the selected potent immunosuppressants azathioprine, 6-
tofacitinib	compatible with	mercaptopurine, cyclosporine or tacrolimus (as identified by
	tofacitinib	ATC code[s]) during the follow-up period.
		Complete list of selected potent immunosuppressants in
		ANNEX 7. LIST OF ATC CODES FOR MEDICATIONS
		OF INTEREST TO AVOID WHILE TAKING
		TOFACITINIB.
Receipt of a live	Outcome:	Defined as ≥1 CCAM procedure code or ≥1 ICD 10 code
vaccination while	Concomitant	and/or ≥1 prescription reimbursement (as identified by ATC
taking tofacitinib	medications not	code[s]) for a live vaccination (as available) while receiving
-	compatible with	tofacitinib therapy in the follow-up period.
	tofacitinib	Complete list of vaccinations in ANNEX 4. LIST OF ATC
		CODES FOR COMEDICATIONS OF INTERESTANNEX
		4. LIST OF ATC CODES FOR COMEDICATIONS OF
		INTEREST.

9.3.2. Duration of tofacitinib therapy

Duration of tofacitinib therapy will be defined as the time from the date of the index tofacitinib dispensing to the date of discontinuation of tofacitinib. The operational definitions for duration of tofacitinib therapy will be further elaborated in the SAP. For example, the following proxy may be used to estimate duration, that is, time between 2 prescription dispensing of tofacitinib, allowing for a grace period of a pre-determined length (e.g., 90 days) before being considered to have discontinued tofacitinib. The length of the grace period will be determined during development of the SAP.

9.3.3. Average daily dose

Drug reimbursement data will be utilised to estimate tofacitinib ADD (in mg per day) for each patient and duration of treatment. ADD will be described in each 8-week period, based on the posology and recommended duration of use in the SmPC, during the follow-up period for a total of six 8-week periods.

ADD will be calculated by total dose dispensed during an 8-week period divided by the length of the 8-week period, 56 days. Dose per prescription will be determined by the dose per tablet multiplied by the number tablets on packaging. Total dose dispensed is the sum of doses from all prescriptions in an 8-week period. If a prescription spans across 2 or more 8-week periods, the dose of the prescription will be prorated across periods.

ADD will be calculated from Week 1 through Week 48. For each 8-week period, ADD will be described as a continuous and categorical variable as below:

- Up to 5 mg ADD;
- >5 mg to 11 mg ADD;
- >11 mg to 15 mg ADD;
- >15 to 20 mg ADD; and
- >20 mg ADD.

ADD may be further stratified by (pending sufficient sample size):

- Approved indication, or by the indication groups: "PsA or RA" and "UC";
- Presence of ≥1 major VTE risk factors prior to tofacitinib initiation;
- Use of an alternative therapy (i.e., biologic) in the 12 months prior to tofacitinib initiation; and
- VTE Reporting Period (1, 2, and 3), depending on the objective.

• The operational definitions for ADD will be further elaborated in the SAP.

